12.4.1.3 Information to be included in the written information

The written information should include at least the following information as required by Clause 1 of Article 51 of the GCP Ordinance:

- (1) That the clinical trial involves research
- (2) The purpose of the clinical trial
- (3) The name, title, and contact information of the investigator or subinvestigator
- (4) Trial methods (including the research aspects of the trial, subject selection criteria)
- (5) The expected clinical benefits and risks or inconveniences
- (6) The availability of alternative treatments for the target disease in this clinical trial and their important potential benefits and risks
- (7) The expected duration of the subject's participation in the clinical trial
- (8) That the subject's participation in the clinical trial is voluntary and that the subject may refuse to participate or withdraw from the clinical trial, at any time, without penalty or loss of benefits to which the subject is otherwise entitled
- (9) That the CRA, the auditors, the institutional review board (IRB), and the regulatory authorities will be granted direct access to the subject's medical information, without violating the confidentiality of the subject, and that by signing an informed consent form, the subject is authorizing such access.
- (10) That the subject's privacy will remain confidential even if the results of the clinical trial are published

- (11) The contact information of the study center for further information regarding the clinical trial and the rights of the subject and for inquiry or contact in the event of trial-related injury
- (12) The compensation and/or treatment available to the subject in the event of trial-related injury
- (13) The type of the institutional review board that investigates and reviews the appropriateness, etc. of the clinical trial; the matters that are investigated and reviewed in each institutional review board; and other matters regarding the institutional review board in relation to the clinical trial. That the subject can see the procedures, etc. of the institutional review board.
- (14) The planned number of subjects involved in the clinical trial
- (15) That the subject will be informed in a timely manner if information becomes available that may be relevant to the subject's willingness to continue participation in the clinical trial
- (16) The foreseeable circumstances and/or reasons under which the subject's participation in the clinical trial may be terminated
- (17) The anticipated expenses, if any, to the subject for participating in the clinical trial
- (18) The anticipated prorated payment, if any, to the subject for participating in the clinical trial
- (19) The subject's responsibilities
- (20) Other necessary matters in relation to the protection of the human rights of the subject

12.4.1.4 Method of obtaining informed consent

- (1) Prior to the participation of each subject in the clinical trial, the investigator or subinvestigator will fully explain the contents of the trial to the subject by using the written information approved by the institutional review board to obtain written consent of his/her own free will from the subject.
- (2) The investigator or subinvestigator should provide the subject ample time and opportunity to inquire about details of the trial and to decide whether or not to participate in the trial before obtaining informed consent from the subject. At this time, the investigator or subinvestigator, or the clinical trial collaborator should answer all questions about the trial to the satisfaction of the subject.
- (3) The investigator or subinvestigator who provided explanations and the subject should affix their names and seals to or sign, and date the informed consent form. If a clinical trial collaborator provided supplemental explanations, the clinical trial collaborator should also affix his/her name and seal to or sign, and date the informed consent form.
- (4) After obtaining informed consent for the participation in the clinical trial from the subject, unless otherwise stipulated by the study center, before the participation of the subject in the trial, the investigator or subinvestigator should immediately provide a

copy of the informed consent form and the written information to the subject after retaining the informed consent form with their names and seals, or signatures, and date (such as by affixing the form on the medical record) and recording the date of informed consent on the case report form.

- (5) The investigator or subinvestigator should ask whether the subject is being treated by any primary physician. If the subject is being treated by his/her primary physician, the investigator or subinvestigator should inform the primary physician of the participation of the subject in the trial before the start of investigational drug administration with the subject's consent. In addition, the name and the medical institution of the primary physician and the date of report should be recorded in the medical record.

12.5 Protection of the Privacy of Subjects

With regard to the conduct of this clinical trial, due consideration will be given to the protection of the privacy of subjects at the time of handling of their case report forms, informed consent forms, source documents, and other data including the personal information of the subjects as well as at the time of publication of the clinical trial results.

The investigator or subinvestigator should use subject identification codes and not use medical record numbers when entering any information that can identify individual subjects on the case report forms, etc. If other documents or materials (laboratory test slips, packages of the investigational drug, etc.) include any information that can identify individual subjects, such as subject name, such information should be masked so that individual subjects cannot be identified before submission of the document or material to the sponsor.

The investigator or subinvestigator will inform subjects that the monitors, the auditors, the institutional review board (IRB), and the regulatory authorities pay due attention to the confidentiality of subjects with respect to their personal information obtained through direct access to source documents, etc. and their personal information provided at the time of drug marketing (importing) approval application.

The investigator will prepare and retain a subject identification code list (including subject names corresponding to subject identification codes) that is used to identify individual subjects.

13. FINANCING

13.1 Compensation for Health Injury and Insurance

- (1) If a subject suffers any injury directly resulting from the use of the study drug or a study procedure (“trial-related health injury”), the study center will provide the subject with adequate treatment and other appropriate measures. Among the medical expenses required for the treatment, the sponsor will pay for medical expenses that are not covered by the health insurance, provided the subject has followed the directions given by the Investigator, and the trial-related health injury is not due to the natural progression of any condition existing before the subject participated in the study. No other compensation will be offered.
- (2) If any trial-related health injury occurs and results in legal liability, except when the study center is liable, the sponsor will be legally liable to the trial-related health injury. If it is not clear who will be legally liable to the trial-related health injury, the study center and the sponsor should discuss in good faith to solve the issue.
- (3) The sponsor has taken out an insurance policy to cover trial-related health injury.
- (4) If any health injury results from the intention or negligence of a subject or a study center, the health injury should be discussed based on the trial contract.

13.2 Payments to Subjects and Planned Trial-related Expenses

Any expense for testing or diagnostic imaging for a subject during the trial period will be paid by the sponsor as an expense for medical treatment designed for evaluation. Expenses such as transportation expenses for a subject should be paid with approval of the institutional review board after discussion by the study center and the sponsor. Methods for payment will be discussed with the study center and determined.

14 PUBLICATION POLICY

14.1 Use of the Data on this Clinical Trial

All of unpublished information that was provided by the sponsor related to the investigational drug, including but not limited to clinical applications, formulation, manufacturing method and other academic data should be treated as confidential. Investigator can use the information only for the purposes of this trial. In addition, all information about the trial, including the study results, is the confidential information of the sponsor. If you want to use for any purpose other than this trial, or disclose to a third party, you must obtain written consent from the sponsor previously.

14.2 Publication of the Trial Results

Any of the information obtained in this study, it is not allowed to publish without prior consultation with the sponsors. For the method of the publication, the sponsor will determine after the end of the trial.

Sponsor is committed to honoring the principles of academic freedom while, at the same time, protecting its confidential information, the subjects, and the integrity of the study, and the study documentation all in compliance with applicable law. Institution and/or Investigator recognize that, with respect to any study that is part of a multi-site study, there is a need for a coordinated approach to any publication or presentation of results from the sites. Accordingly, the Institution/Investigator shall not publish or present any results from this study to any third parties until: (1) Sponsor publishes the results; (2) Institution and/or Investigator receives written notification from Sponsor that publication of the results is no longer planned; or (3) twelve (12) months following the close of Study, whichever occurs first.

Institution and/or Investigator shall submit to Sponsor for its review a copy of any proposed publication at least thirty (30) calendar days prior to the planned date of submission for publication or presentation. Institution and Investigator shall consider in good faith all comments received from Sponsor during the review period and shall delete Sponsor's confidential information (other than study results).

If Sponsor determines that the publication contains patentable subject matter which requires protection, Sponsor may require the delay of submission for publication or presentation for an additional period of time for the purpose of filing patent applications or otherwise take measures to protect such information.

Institution and/or the Investigator shall acknowledge Sponsor's support in all publications and presentations.

15. PLANNED TRIAL PERIOD

January 1, 2016 (IRB submission) to March 31, 2017 (Data lock)


APPENDIX 1

Trial Schedule (Examinations, Observations, Tests, and Evaluations and their Timing)

Trial period	Screening	Treatment ^a												Follow-up
	Day -21 to the day before Week 1	Week 1 (baseline)	Week 2	Week 3	Week 4	Week 5	Week 6	Week 7	Week 8	PK1	PK2	PK5	Week 9 (Study completion) ^b	Week 12 (Study completion) ^c
Informed consent	X													
Inclusion/exclusion criteria	X	X												
Assignment of subject number	X													
Medical history	X													
Age, sex,	X													
CT Scan (densitometry)	X ^d													
Physical examination (excluding breast and urogenital examination)	X												X	X
Body height	X													
Body weight	X	X ^e				X ^e								
Blood sampling for viral safety assessment ^f		X												
Urine pregnancy test (Only in women of childbearing potential)	X					X							X	X
Urinary cotinine level	X					X							X	X
Blood and urine sampling for laboratory tests (Hematology, blood chemistry, urinalysis)	X	X ^g				X ^g							X	X
Vital signs (Pulse rate, blood pressure, respiratory rate, body temperature) ^h		X	X	X	X	X	X	X	X				X	X
12-lead ECG	X	X											(X)	
Pulmonary function tests before and after administration of a bronchodilator (FEV ₁ and FVC) ⁱ	X ⁱ					X ⁱ							X ⁱ	X ⁱ
Blood sampling for alpha ₁ -PI concentration measurement	X ^j	X ^g						X ^g	X ^k	X ^k	X ^k	X ^k	X ^k	
Intravenous infusion of Alpha-1 MP ^l		X	X	X	X	X	X	X	X					
Observation of subjects after infusion of Alpha-1 MP ^m		X	X	X	X	X	X	X	X					
Evaluation of COPD exacerbations	X	X	X	X	X	X	X	X	X	X	X	X	X	X
Evaluation of adverse events	X	X	X	X	X	X	X	X	X	X	X	X	X	X
Evaluation of concomitant medications	X	X	X	X	X	X	X	X	X	X	X	X	X	X

- a: The date of individual visits will be determined in relation to the date of the Week 1 (baseline) visit. The date of all visits after the screening visit and the Week 1 (baseline) visit will be arranged within a time window of ± 1 day. The PK evaluation period will start at the Week 8 visit and end at the Week 9 visit.
- b: At the Week 9 visit, subjects will be asked whether or not they would like to enter the extension trial (GTI1401-OLE). For subjects eligible for participation in the extension trial, the Week 9 visit will be the study completion visit for this clinical trial (GTI1401).
- c: Subjects not entering the extension trial (GTI1401-OLE) and subjects who receive Alpha-1 MP at any dose and discontinue this clinical trial early will be asked to return to the study center for the follow-up/study completion procedures and evaluations scheduled at the Week 12 visit. This visit should be made at the timing as close as possible to 4 weeks (i.e., 30 days) after the last dose of the investigational drug in the subject.
- d: CT densitometry scan should be performed anytime from the Screening Visit to the Week 1 (Baseline) Visit; if the CT densitometry scan is performed at the Week 1 (Baseline) Visit, then it must be performed prior to the first Alpha-1 MP infusion. This CT scan will measure lung density.
- e: Body weight will be used to calculate the Alpha-1 MP dose, and this recorded body weight will be used for dose calculation until the next scheduled body weight measurement.
- f: Blood samples for viral safety assessment (viral NAT and viral serologic test) will be collected before the intravenous infusions of Alpha-1 MP at the Week 1 (baseline) visit. However, the collected samples will be tested only if the subject shows clinical signs or symptoms suggestive of viral infection during the trial period. Only in this case will additional blood samples for viral NAT and viral serologic test be collected. All these collected blood samples will be stored until completion of all the tests in this clinical trial (GTI1401) and the extension trial (GTI1401-OLE).
- g: Sampling will be performed before each intravenous infusion of Alpha-1 MP.
- h: Vital signs will be checked immediately before and after each intravenous infusion of Alpha-1 MP.
- i: Pulmonary function tests after administration of a bronchodilator will be performed 15 to 30 minutes after administration of a bronchodilator. For a short-acting bronchodilator, subjects will receive 4 puffs of salbutamol given by an MDI and spacer in each pulmonary function testing. The same bronchodilator as that used at the start of the trial should be used throughout the trial period.
- j: Sampling will be performed in subjects with no previously documented alpha1-PI levels as measured by nephelometry (if it is unknown whether the subject's alpha1-PI level is <50 mg/dL or not).
- k: Sampling time points of PK samples: 1) Immediately before the intravenous infusion; 2) Immediately after the intravenous infusion (after flushing the infusion line with physiological saline) (at 0 hours); 3) At 15 minutes after completion of the intravenous infusion; 4) At 2 hours after completion of the intravenous infusion; 5) At 4 hours after completion of the intravenous infusion; 6) At 8 hours after completion of the intravenous infusion; 7) At 24 ± 4 hours (1 day after completion of the intravenous infusion); 8) At 48 ± 4 hours (2 days after completion of the intravenous infusion); 9) At $120 \text{ hours} \pm 1 \text{ day}$ (5 days after completion of the intravenous infusion); and 10) At $168 \text{ hours} \pm 1 \text{ day}$ (7 days after completion of the intravenous infusion) (Week 9).
- l: Weekly intravenous infusions of 60 mg/kg of Alpha-1 MP will be given under the supervision of the investigator or a designated person at each study center.
- m: Subjects will be observed for at least 30 minutes after each intravenous infusion of Alpha-1 MP.

APPENDIX 2

A2.1 Sponsor

1) Sponsor

[REDACTED]
Grifols Japan K.K.
[name]
[name]
TEL: [REDACTED] FAX: [REDACTED]

2)

[REDACTED]
Grifols Japan K.K.
[name]
[name]
TEL: [REDACTED] FAX: [REDACTED]

3)

[REDACTED]
Japan Anti-Tuberculosis Association
[name]
TEL: [REDACTED] FAX: [REDACTED]

<Main duties>

To give the sponsor medical advice on the following matters when necessary:

- (i) Appropriateness of the investigational plan, the protocol, etc.
- (ii) Action to be taken against adverse events and evaluation of them
- (iii) Appropriateness of subject data handling and result assessment after completion of the trial
- (iv) Appropriateness of the clinical study report
- (v) Other medical issues concerning the trial

A2.2 Contract Research Organization

In this clinical trial, trial-related duties will be entrusted to the contract research organization below:

CMIC HOLDINGS Co., Ltd.
[REDACTED]
[name]
[contact] (main switchboard)

Monitor (CRA) and Medical Monitor

Refer to Attachment.

<Main duties>

- (i) Duties related to the selection of study centers and investigators
- (ii) Duties related to negotiations and confirmation with investigators and study centers

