4.2.2 Exclusion Criteria

1. Subjects with moderately or severely deteriorated lung function in the 4 weeks before the Week 1 (baseline) visit
2. Subjects whose percentage of forced expired volume in 1 second (%FEV₁) after inhalation of a bronchodilator is <30% during the screening period
3. Subjects who have undergone lung transplantation or liver transplantation
4. Subjects who have undergone any lung surgery (excluding lung biopsy) in the past 2 years
5. Subjects with increased liver enzymes (AST, ALT, and ALP) ≥ 2.5 times the upper limit of normal
6. Subjects with severe complications including but not limited to congestive heart failure and liver cirrhosis
7. Subjects who have developed any malignant tumor (including malignant melanoma; however, other forms of skin cancer are excluded) in the past 5 years
8. Pregnant women, breastfeeding women, or women of childbearing potential who do not intend to use effective contraceptive methods (use of oral, injection, or implant hormonal contraceptives; placement of an intrauterine device (IUD) or intrauterine contraceptive system; concomitant use of spermicidal foam, gel, film, cream, suppository and condoms or cervical caps; male sterilization; or abstinence) throughout the trial period or male subjects who have a partner who is of childbearing potential and is unwilling to use effective contraceptive methods throughout the trial period.
9. Subjects with a past history of HAV, HBV, HCV, or HIV infection, or subjects currently presenting with clinical signs or symptoms suggestive of such infection
10. Subjects with a smoking history in the past 6 months, or subjects tested positive for urinary cotinine levels at the screening visit
11. Subjects participating in another clinical trial within 4 weeks before the Week 1 (baseline) visit
12. Subjects with a history of anaphylactic or severe systemic reactions to any plasma derived alpha₁-PI product or other blood products
13. Subjects who have continuously received any systemic steroid therapy at a prednisone-equivalent dose >5 mg/day within 4 weeks before the Week 1 (baseline) visit (Note: inhaled steroids are not regarded as systemic steroids)
14. Subjects who have used any systemic or aerosolized antibiotic drug for the treatment of COPD exacerbation within 4 weeks before the Week 1 (baseline) visit

15. Subjects with a previous or current diagnosis of selective, severe IgA deficiency

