16. Subjects who are mentally challenged and cannot independently give consent
17. Subjects who have difficulty in adhering to the protocol or its procedures in the opinion of the investigator
18. Subjects who have medical conditions that may confound the results of this clinical trial or may endanger other subjects during the participation in this clinical trial in the opinion of the investigator

<Rationale for establishing the exclusion criteria>

1. This criterion has been established to exclude subjects with this medical condition because the condition will affect pulmonary function tests (PFTs) and clinical laboratory tests, thereby precluding appropriate safety evaluation.
2. This criterion has been established to determine the range of percentage of forced expired volume in 1 second (%FEV₁) to be excluded.
3. Same as 1 above.
4. Same as 1 above.
5. This criterion has been established to exclude subjects with any underlying disease that may affect clinical laboratory values and safety evaluation.
6. Same as 5 above.
7. Same as 5 above.
8. This criterion has been established because animal reproduction studies have not been conducted with Alpha₁-PI, the safety of Alpha₁-PI in pregnant women and their fetuses as well as its effects on fertility have not been established yet, and no results on the excretion of Alpha₁-PI into breast milk are available.
9. Same as 1 above.
10. This criterion has been established to exclude smokers who may be at risk for further deterioration of lung function and lung damage.
11. This criterion has been established to exclude any effect on the evaluation of adverse events and safety of this investigational drug.
12. Same as 11 above.
13. This criterion has been established to reduce clinical changes associated with the use of concomitant drugs and exclude factors that may affect symptomatic improvement.
14. Same as 1 above.
15. Same as 11 above.
16. This criterion has been established to exclude subjects in whom it is difficult to confirm whether they intend to consent or not.
17. This criterion has been established to exclude subjects who cannot adhere to the protocol.
18. Same as 11 above.

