4.4.3 Schedule for Investigational Drug Administration to Each Subject

Subjects will receive a total of 8 IV infusions of 60 mg/kg Alpha-1 MP administered weekly. Weekly infusions of Alpha-1 MP will be performed at the Investigator's study site under the care and supervision of the treating Investigator, or designee, during scheduled study visits at Weeks 1 (Baseline), 2, 3, 4, 5, 6, 7, and 8. Subjects will receive their first infusion of Alpha-1 MP at the Week 1 (Baseline) Visit and their last infusion at the Week 8 Visit.

Each week, designated study site personnel will prepare an infusion bag of Alpha-1 MP at the calculated volume based on the subject's body weight, and the subject will receive the contents of the infusion bag via IV administration.

The prescribed infusion rate for Alpha-1 MP is not to exceed 0.08 mL/kg/min as determined by the response and comfort of the subject. The recommended dose for this trial takes approximately 15 minutes per IV bag to infuse (based on ~70 kg subject). After completion of the infusion bag, each subject will receive a minimum of 25 mL of 0.9% Sodium Chloride for Injection to flush the IV line.

For each infusion, the total infusion volume prepared, total infusion time, total volume infused, and, if necessary, any infusion interruption with explanation will be documented.

Complete details are provided in the Pharmacy Manual.

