4.7.2 Observation and Measurement

The trial procedures and evaluations at each visit are described below. For a summary of the scheduled visits and the trial procedures and evaluations at each visit, refer to Appendix 1 “Trial Schedule.” Unscheduled visits may be requested for subjects to ensure their safety if necessary.

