4.7.2.1 Screening period

Prior to collection of screening evaluation data or the start of the trial, written consent must be obtained from all candidate subjects. Trial entry will start after the subjects sign their informed consent forms. Subject eligibility will be evaluated during the screening period.

The screening visit will occur within 3 weeks before the Week 1 (baseline) visit.

Visit	Trial Procedures and Evaluations
Screening (within 3 weeks)	
• Informed consent• Eligibility evaluation based on the inclusion/exclusion criteria• PFT (FEV₁ and FVC) before and after administration of a bronchodilator (refer to Section 4.6.2)• Assignment of subject numbers• Medical history• Age, sex,• CT scan (This CT scan [densitometry] will be performed for documentation of emphysema at each study site, and CT scan data will be evaluated centrally for lung density at Vida Diagnostics, Inc.; see CT Scan Manual for detailed procedures)• Body height

	
 • Body weight • Physical examination (excluding breast and urogenital examination) • Laboratory tests (refer to Section 4.7.3) 
 Urine samples: Urinalysis 
 Urine pregnancy test: To be performed only in women of childbearing potential. Only women tested negative for pregnancy can continue the trial. Urinary cotinine level: Subjects tested positive for urinary cotinine are considered ineligible. Blood samples: Blood chemistry, hematology • Alpha₁-PI measurement: To be performed in subjects with no previously documented alpha₁-PI levels as measured by nephelometry (if it is unknown whether the subject's alpha₁-PI level is <50 mg/dL or not) • COPD exacerbation (refer to Section 4.6.1) • Adverse events (AEs) • Concomitant medications • 12-lead ECG
--	--

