4.7.2.2 Treatment period

During the 8-week treatment period, subjects will receive a total of 8 weekly intravenous infusions of 60 mg/kg of Alpha-1 MP. Weekly infusions of Alpha-1 MP will be given at the scheduled Week 1 (baseline), 2, 3, 4, 5, 6, 7, and 8 visits at each study center. Visit dates after the Week 1 (baseline) visit will be arranged at 1-week intervals as specified in the protocol according to the actual date of the Week 1 (baseline) visit (± 1 day).

Subjects meeting all of the inclusion criteria and not meeting any of the exclusion criteria will make the Week 1 (baseline) visit within 21 days after the screening visit. Subjects considered eligible will receive the initial intravenous infusion (intravenous drip) of Alpha-1 MP at the Week 1 (baseline) visit.

The 1-week PK evaluation period will start at the Week 8 visit and end at the Week 9 visit. At the Week 8 visit, subjects will undergo blood sampling for PK evaluation immediately before the intravenous infusion of Alpha-1 MP; immediately after the intravenous infusion; and at 15 minutes, 2, 4, and 8 hours after completion of the intravenous infusion. Subjects will visit the study center 1 day (PK1), 2 days (PK2), and 5 days (PK5) after the Week 8 visit to provide PK evaluation blood samples at 24 ± 4 hours (1 day), 48 ± 4 hours (2 days), and 120 hours ± 1 day (5 days), respectively, after the intravenous infusion of Alpha-1 MP at the Week 8 visit. The date of Week 9 visit will be scheduled in the week specified in the protocol according to the actual date of the Week 1 (baseline) visit (± 1 day).

Visit	Trial Procedures and Evaluations

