Week 1 (Baseline)	
[Before intravenous infusion of Alpha-1 MP]
 
 
• Reevaluation of the inclusion/exclusion criteria 
• Body weight: Recorded body weight will be used to calculate the Alpha-1 MP dose administered at the Week 1 (baseline) visit. This recorded body weight will be used for dose calculation until the next scheduled body weight measurement. 
• Laboratory tests (refer to Section 4.7.3) 
Urine samples: Urinalysis
 
Blood samples:
 
Viral safety assessment: Blood samples for viral nucleic acid amplification (NAT) and viral serologic test will be collected at the Week 1 (baseline) visit. However, the collected samples will be tested only if the subject shows clinical signs or symptoms

	
suggestive of viral infection during the trial period. All collected blood samples will be stored until completion of the tests in this clinical trial (GTI1401) and the extension trial (GTI1401-OLE).
 
Blood chemistry, hematology, alpha₁-PI concentrations
 
 • COPD exacerbation (refer to Section 4.6.1) • Adverse events • Concomitant medications • Vital signs (pulse rate, blood pressure, respiratory rate, and body temperature) immediately before the start of intravenous infusion of Alpha-1 MP 
[At the time of intravenous infusion (intravenous drip) of Alpha-1 MP]
 
 • Intravenous infusion of Alpha-1 MP • Vital signs (pulse rate, blood pressure, respiratory rate, and body temperature) immediately after the completion of intravenous infusion of Alpha-1 MP • 12-lead ECG immediately after the end of intravenous infusion of Alpha-1 MP • Observation of the subject for at least 30 minutes after the intravenous infusion

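### No pregnancy test is scheduled at Week 1, so the only test before first infusion is 1 to 21 days old; adding one is a cheap, minor improvement

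*Protocol*

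**What the plan says.** The schedule row that begins "Urine pregnancy test (Only in women of childbearing potential" in Protocol Appendix 1 has marks at Screening, Week 5, Week 9 and Week 12 only. SAP Appendix 1 repeats it. The visit tables match: Screening, Week 5, Week 9 and Week 12 list the test, while Week 1 lists urinalysis as its only urine test.

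At Screening the test is a gate: "To be performed only in women of childbearing potential. Only women tested negative for pregnancy can continue the trial". The Week 5 table and Table 4-2 carry the same rule. On timing, section 4.7.2.2 says eligible subjects "will make the Week 1 (baseline) visit within 21 days after the screening visit", and Appendix 1 ends the screening period on the day before Week 1. Before the Week 1 infusion the site carries out a "Reevaluation of the inclusion/exclusion criteria", and no pregnancy test is attached to that step.

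Exclusion criterion 8 covers "Pregnant women, breastfeeding women, or women of childbearing potential who do not intend to use effective contraceptive methods". Its rationale is that "animal reproduction studies have not been conducted with" the product and that safety in pregnancy is not established. Section 5.1 bars pregnant women from entry and requires withdrawal of a subject who becomes pregnant. On dosing, section 4.4.3 states: "Subjects will receive a total of 8 IV infusions of 60 mg/kg Alpha-1 MP administered weekly".

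**The concern.** Pregnancy is an exclusion criterion that can change status between screening and first dose. At Week 1 the protocol asks the site to check the criteria again and repeats blood chemistry, hematology, urinalysis, body weight and ECG, but not the pregnancy test. A pregnancy too early to show at screening, or begun soon after it, may be detectable by Week 1. On the current schedule it would be found at Week 5 unless someone suspected it sooner.

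What is at stake is the protection of individual subjects: exposure of a pregnancy to a product whose safety in pregnancy is not established, when the protocol intends to exclude such exposure.

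**Working it through.** The plan gives no figure of its own for test age or test interval, so everything here is counted from the schedule.

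**Inputs**
- Screening window: Day -21 to the day before Week 1 (Protocol Appendix 1; section 4.7.2.2 gives the same 21-day limit).
- Pregnancy tests: Screening, Weeks 5, 9 and 12 (Protocol Appendix 1, SAP Appendix 1, visit tables).
- Infusions: weekly, Weeks 1 to 8, 60 mg/kg each (section 4.4.3).
- The Week 5 test is listed among the procedures before the Week 5 infusion (section 4.7.2.2).
- Visits after Week 1 have a window of ±1 day relative to the Week 1 date (Appendix 1, note a).

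**Age of the last test at first infusion** = Week 1 date minus screening date.
- Now: minimum 1 day, maximum 21 days.
- With a Week 1 test before dosing: 0 days.

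**Longest gap between scheduled tests up to Week 5.** This is the like-for-like measure, because adding a test splits one interval into two.
- Now there is one interval, Screening to Week 5. Week 5 is 28 ± 1 = 27 to 29 days after Week 1, so the interval runs from 1 + 27 = 28 days to 21 + 29 = 50 days.
- With the change there are two intervals: Screening to Week 1 (1 to 21 days) and Week 1 to Week 5 (27 to 29 days). The longest is at most 29 days.

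**Infusions before the Week 5 test**
- Weeks 1, 2, 3 and 4: 4 of 8 infusions, or 4 × 60 = 240 mg/kg of 8 × 60 = 480 mg/kg.
- For a pregnancy detectable at Week 1 and not otherwise suspected, the change reduces exposure from as many as four infusions to none.
- For a conception too recent to show at Week 1, or a later one, nothing changes: up to four infusions can still precede the Week 5 test.

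**Is the blank Week 1 cell an extraction fault?** No. Two schedule tables and the separate visit tables agree.

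**The case against.** The case for leaving the schedule alone is substantial. The documents are consistent, and no passage sets a maximum test age at dosing. The protocol chose a gate at screening followed by periodic tests, and urinary cotinine follows the same visits. Criterion 8 requires the intention to use effective contraception throughout the trial, and section 4.7.1 counts participation from the start of screening, so the commitment covers the 1 to 21 days in question. The Week 1 re-evaluation makes pregnancy a required question before dosing. Subjects are seen weekly, section 4.7.2 adds "Unscheduled visits may be requested for subjects to ensure their safety if necessary", and section 5.4.2 requires withdrawal and follow-up once a pregnancy is known.

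Most of this stands, and it makes the residual risk low. It does not close the gap entirely. The contraception commitment does not reach back before entry, so a conception shortly before screening could test negative then and positive at Week 1. Unscheduled visits and withdrawal depend on someone suspecting or detecting the pregnancy. The re-evaluation asks about pregnancy status with no current test result behind it.

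A reader might infer that the schedule breaks the protocol's own rules. It does not: re-evaluating the criteria is not stated to mean repeating the screening tests.

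**Conclusion.** The point holds as a minor, inexpensive improvement. At first infusion the last negative test is 1 to 21 days old, and no scheduled test looks for a pregnancy that has become detectable by then. A Week 1 test brings that age to 0 days and shortens the longest gap between tests up to Week 5 from at most 50 days to at most 29.

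Three stronger conclusions are tempting and not supported:
- **That a Week 1 test removes the four-infusion interval.** It does not. Four infusions still separate Weeks 1 and 5, so 240 mg/kg is the most that could be avoided, and only for a pregnancy detectable at Week 1.
- **That the product is known to harm a fetus.** The protocol states an absence of data, not a known hazard.
- **That the trial's results are affected.** No endpoint or analysis depends on this test.

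The schedule facts are certain; the practical weight is not. It depends on how many women of childbearing potential enrol, which the documents do not state. With a target of at least 3 subjects (section 8.2), that number could be zero. The figures assume visits keep to the stated windows, and test age is not the same as certainty about pregnancy status.

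**What to change.** Add a local urine pregnancy test at Week 1, for women of childbearing potential, in three places: Protocol Appendix 1, the Week 1 visit table in section 4.7.2.2, and SAP Appendix 1. Run it on the urine already collected before the Week 1 infusion and require a negative result before dosing, reusing the continuation rule from the Screening and Week 5 tables. The SAP pregnancy listing (11.7) is laid out by visit, so its shell needs no redesign.

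The cost is one local test per woman of childbearing potential, with no added visit or blood draw. Table 4-2 sends urinalysis to the central laboratory and the pregnancy test to the local one, so a portion of the Week 1 urine must stay on site. The first infusion also waits for the local result. The wait should be short, but the documents give no turnaround time. The test will still miss very recent conceptions.
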